### 3. Age and Reproductive Status

- a) Males and Females, ages  $\geq 18$  years.
- b) Women of childbearing potential (WOCBP) must have a negative serum or urine pregnancy test (minimum sensitivity 25 IU/L or equivalent units of HCG) within 24 hours prior to the start of study drug.

- c) Women must not be breastfeeding.
- d) WOCBP must agree to follow instructions for method(s) of contraception for the duration of treatment with nivolumab plus 5 half-lives of nivolumab (19 weeks) plus 30 days (duration of ovulation cycle) for a total of 23 weeks post-treatment completion.
- e) Males who are sexually active with WOCBP must agree to follow instructions for method(s) of contraception for the duration of treatment with nivolumab plus 5 half-lives of the study drug (19 weeks) plus 90 days (duration of sperm turnover) for a total of 31 weeks days post-treatment completion.
- f) Azoospermic males and WOCBP who are continuously not heterosexually active are exempt from contraceptive requirements. However they must still undergo pregnancy testing as described in this section.

Investigators shall counsel WOCBP and male subjects who are sexually active with WOCBP on the importance of pregnancy prevention and the implications of an unexpected pregnancy. Investigators shall advise WOCBP and male subjects who are sexually active with WOCBP on the use of highly effective methods of contraception. Highly effective methods of contraception have a failure rate of < 1% when used consistently and correctly.

At a minimum, subjects must agree to the use of two methods of contraception, with one method being highly effective and the other method being either highly effective or less effective as listed below:

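### The male post-treatment contraception total in Protocol inclusion item 3e (31 weeks) is 6 days shorter than the parts it is built from (19 weeks plus 90 days, or 223 days)

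*Protocol*

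**What the plan says.** Protocol Section 3.3.1 (Inclusion Criteria), under Age and Reproductive Status, gives two parallel contraception periods, each with its parts and a total.

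- **Item 3e (men who are sexually active with women of childbearing potential).** Contraception instructions are to be followed "for the duration of treatment with nivolumab plus 5 half-lives of the study drug (19 weeks"), and then "plus 90 days (duration of sperm turnover) for a total of 31 weeks days post-treatment completion".
- **Item 3d (women of childbearing potential).** The period is the duration of treatment "plus 5 half-lives of nivolumab (19 weeks) plus 30 days (duration of ovulation cycle) for a total of 23 weeks post-treatment completion".

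Both items use the same 19-week figure for drug washout. They differ in the second part: 30 days for an ovulation cycle, 90 days for sperm turnover. Neither item states a rounding rule, and the available text gives no other male total.

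**The concern.** Item 3e shows its own sum, and the total does not match it. The unit is also garbled, with weeks and days printed side by side after a single number. The total cannot be 31 days, because that is less than the 90-day part alone. That leaves 31 weeks, which falls short of 19 weeks plus 90 days.

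This is a commitment that a subject must accept in order to enrol, and the end of Section 3.3.2 asks that every eligibility criterion be fully met. Investigators must also counsel male subjects on pregnancy prevention. A site needs one end date for that conversation, and this sentence supports two. The single summary number is the one most easily carried into counselling notes or other study documents, and it is the shorter of the two. The statistical content of the trial is not at stake.

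**Working it through.** **Inputs, all from Protocol Section 3.3.1, items 3d and 3e**

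- Washout part (five half-lives): 19 weeks
- Sperm-turnover part: 90 days
- Stated male total: 31 weeks, after setting aside the stray unit word
- Comparator, female item: 19 weeks plus 30 days, stated total 23 weeks

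**Step 1: sum the male parts.** 19 × 7 + 90 = 133 + 90 = 223 days. In weeks, 223 / 7 = 31.86, which is 31 weeks and 6 days.

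**Step 2: compare with the stated total.** 31 × 7 = 217 days. The shortfall is 223 − 217 = 6 days, and 6 / 223 = 2.7%.

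**Step 3: try to reproduce 31 by rounding, with the female item as a check.**

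| Item | Sum (days) | Sum (weeks) | Rounded down | Nearest | Rounded up | Stated |
|---|---|---|---|---|---|---|
| 3d, women | 133 + 30 = 163 | 23.29 | 23 | 23 | 24 | 23 |
| 3e, men | 133 + 90 = 223 | 31.86 | 31 | 32 | 32 | 31 |

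The female total is 161 days against 163, so it is 2 days under its parts but correct to the nearest week. The male total is reproduced only by rounding down.

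**Step 4: ask whether 19 weeks could itself be a rounded figure that hides an exact match.** A total of exactly 217 days would need five half-lives of 217 − 90 = 127 days, or 127 / 7 = 18.14 weeks. That would be written as 18 weeks, not 19.

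Assume instead that 19 weeks stands for any value from 18.5 to 19.5 weeks. This is an assumption; the protocol does not say so.

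- Lower end: 18.5 × 7 + 90 = 129.5 + 90 = 219.5 days
- Upper end: 19.5 × 7 + 90 = 136.5 + 90 = 226.5 days

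Across that range, 217 days is short by 219.5 − 217 = 2.5 days to 226.5 − 217 = 9.5 days.

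**Step 5: ask whether rounding an unrounded sum to the nearest week could give 31.** The sum would have to be below 31.5 weeks, that is 31.5 × 7 = 220.5 days. Five half-lives would then be below 220.5 − 90 = 130.5 days (18.64 weeks). To be written as 19 weeks they must also be at least 129.5 days (18.5 weeks). This leaves a window of 1 day at the bottom of a 7-day range, and nothing in the protocol points to a value there.

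**The case against.** Three arguments can be made for the text.

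**A digit may be missing.** The sum is exactly 31 weeks and 6 days. If a 6 once stood between the two unit words in the total, the sentence would be correct and the odd wording explained. This is an attractive reading, because it accounts for both the garbled unit and the shortfall. It cannot be confirmed from the text available, which is otherwise complete and legible in this sentence. Even if the digit was dropped in drafting, the printed total would still be wrong and need correcting. If it was lost only when the PDF was converted to text, the plan itself would be right, so the point should be checked against the source page.

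**The total may be truncated to whole weeks.** Dropping the part-week gives both 23 for women and 31 for men. This is a plausible account of how 31 arose. However, the protocol states no such rule, and item 3d does not establish it, because 23 is also the nearest whole week. Truncation would explain the number without making it equal its parts. For a minimum protective period, rounding down goes in the wrong direction.

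**The parts govern, and nothing turns on it.** The requirement is spelled out as its parts, and a man who follows them completes the full 223 days. A candidate would agree or decline in the same way under either figure, so who enters the trial is very unlikely to change. This stands, and it is why the point is minor. It does not remove the conflict within the sentence.

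**Conclusion.** The concern holds. As printed, the male contraception total in item 3e does not equal the sum given in the same sentence: 217 days against 223, a shortfall of 6 days or 2.7%. If 19 weeks is treated as a rounded figure (assumed 18.5 to 19.5 weeks), the shortfall is 2.5 to 9.5 days and is never zero.

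The conclusion rests on reading the total as 31 weeks, which the 90-day part forces unless a digit has been lost. It uses no outside source.

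Severity is minor. This is an internal conflict in a safety instruction, not a direction to stop contraception early. It does not touch the endpoints, analysis populations, sample size or analyses.

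**What to change.** In Protocol Section 3.3.1, item 3e, replace the total with 223 days (31 weeks and 6 days). If whole weeks are preferred, use 32 weeks (32 × 7 = 224 days), which exceeds the parts by 1 day and so errs on the protective side. Remove the stray unit word in either case. Deleting that word alone is not enough, because it would leave the 6-day shortfall in place.

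Check whether any other study document carries the male total, and align it if so.

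The cost is one wording correction, which can go into the next amendment, plus any matching text elsewhere. No change to the design or the analysis is needed.

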### **HIGHLY EFFECTIVE METHODS OF CONTRACEPTION**

- Male condoms with spermicide
- Hormonal methods of contraception including combined oral contraceptive pills, vaginal ring, injectables, implants and intrauterine devices (IUDs) such as Mirena® by WOCBP subject or male subject's WOCBP partner. Female partners of male subjects participating in the study may use hormone based contraceptives as one of the acceptable methods of contraception since they will not be receiving study drug
- Nonhormonal IUDs, such as ParaGard®
- Tubal ligation
- Vasectomy.
- Complete Abstinence\*

\*Complete abstinence is defined as complete avoidance of heterosexual intercourse and is an acceptable form of contraception for all study drugs. Subjects who choose complete abstinence are not required to use a second method of contraception, but female subjects must continue to have pregnancy tests. Acceptable alternate methods of highly effective contraception must be discussed in the event that the subject chooses to forego complete abstinence.

### **LESS EFFECTIVE METHODS OF CONTRACEPTION**

- Diaphragm with spermicide
- Cervical cap with spermicide
- Vaginal sponge
- Male Condom without spermicide
- Progestin only pills by WOCBP subject or male subject's WOCBP partner
- Female Condom\*.

\* A male and female condom must not be used together

### **3.3.2 Exclusion Criteria**

#### **1. Medical History and Concurrent Diseases**

- a) Not applicable per Amendment 02: ie, subjects with predominant clear cell histology and prior treatment with an mTOR inhibitor (including, but not limited to, everolimus, temsirolimus, sirolimus, and ridaforolimus) are no longer excluded from this study.
- b) Subjects with any active autoimmune disease or a history of known autoimmune disease. Subjects with vitiligo, type I diabetes mellitus, residual hypothyroidism due to autoimmune condition only requiring hormone replacement, psoriasis not requiring systemic treatment, or conditions not expected to recur in the absence of an external trigger are permitted to enroll.
- c) Any condition requiring systemic treatment with corticosteroids (>10 mg daily prednisone equivalents) or other immunosuppressive medications within 14 days prior to first dose of study drug. Inhaled steroids and adrenal replacement steroid doses >10mg daily prednisone equivalents are permitted in the absence of active autoimmune disease.
- d) Subjects with uncontrolled adrenal insufficiency.
- e) Prior malignancy active within the previous 3 years except for locally curable cancers that have been apparently cured, such as basal or squamous cell skin cancer, superficial bladder cancer, or carcinoma in situ of the prostate, cervix or breast.
- f) Known history of testing positive for human immunodeficiency virus (HIV) or known acquired immunodeficiency syndrome (AIDS).
- g) Any positive test for Hepatitis B or Hepatitis C virus indicating acute or chronic infection.
- h) Known or underlying medical condition (eg, a condition associated with diarrhea or acute diverticulitis) that, in the investigator's opinion, would make the administration of study drug hazardous to the subject or obscure the interpretation of toxicity determination or adverse events.
- i) Major surgery (eg nephrectomy) less than 28 days prior to first dose of study drug. Minor surgery less than 14 days prior to first dose of study drug.
- j) Prior therapy with anti-PD-1, anti-PD-L1, anti-PD-L2, anti-CD137, or anti-CTLA-4 antibody (or any other antibody or drug specifically targeting T-cell co-stimulation or checkpoint pathways); subjects who participated in CA209016 or were randomized in CA209214 are not eligible.

- k) Anti-cancer therapies, including prior treatment with mTOR inhibitor must be discontinued at least 14 days prior to administration of study drug. If patient has received prior bevacizumab, then therapy must have been discontinued at least 21 days prior to administration of study drug. Palliative, focal or whole brain radiation therapy must be discontinued at least 2 weeks before administration of study drug.
- l) All toxicities attributed to prior anti-cancer therapy other than alopecia must have resolved to grade 1 (NCI CTCAE version 4) or baseline before administration of study drug.

## 2. Physical and Laboratory Test Findings

All baseline laboratory parameters should be obtained within 14 days (unless otherwise specified in [Table 5.1-1](#)) of first dose of study drug.

- i) WBC < 2000/ $\mu$ L
- ii) Neutrophil < 1500/ $\mu$ L
- iii) Platelets < 100 x 10^3/ $\mu$ L
- iv) Hemoglobin < 9.0 g/dL
- v) AST > 3.0 x ULN
- vi) ALT > 3.0 x ULN
- vii) Bilirubin > 1.5 x ULN (except subjects with Gilbert Syndrome, who can have total bilirubin < 3.0 mg/dL)
- viii) Serum creatinine of > 2.0 X ULN (upper limit of normal) or creatinine clearance < 30 mL/minute (using Cockcroft/Gault formula)
  - Female CrCl =  $\frac{(140 - \text{age in years}) \times \text{weight in kg} \times 0.85}{72 \times \text{serum creatinine in mg/dL}}$
  - Male CrCl =  $\frac{(140 - \text{age in years}) \times \text{weight in kg} \times 1.00}{72 \times \text{serum creatinine in mg/dL}}$

## 3. Allergies and Adverse Drug Reaction

- a) History of severe hypersensitivity reactions to other monoclonal antibodies.

## 4. Other Exclusion Criteria

- a) Prisoners or subjects who are involuntarily incarcerated.
- b) Subjects who are compulsorily detained for treatment of either a psychiatric or physical (eg, infectious disease) illness.

Eligibility criteria for this study have been carefully considered to ensure the safety of the study subjects and that the results of the study can be used. It is imperative that subjects fully meet all eligibility criteria.

### 3.3.3 *Women of Childbearing Potential*

A Women of childbearing potential (WOCBP) is defined as any female who has experienced menarche and who has not undergone surgical sterilization (hysterectomy or bilateral oophorectomy) and is not postmenopausal. Menopause is defined as 12 months of amenorrhea in

a woman over age 45 years in the absence of other biological or physiological causes. In addition, females under the age of 55 years must have a serum follicle stimulating hormone, (FSH) level > 40mIU/mL to confirm menopause.

\*Females treated with hormone replacement therapy, (HRT), are likely to have artificially suppressed FSH levels and may require a washout period in order to obtain a physiologic FSH level. The duration of the washout period is a function of the type of HRT used. The duration of the washout period below are suggested guidelines and the investigators should use their judgment in checking serum FSH levels. If the serum FSH level is >40 mIU/ml at any time during the washout period, the woman can be considered postmenopausal:

- 1 week minimum for vaginal hormonal products (rings, creams, gels)
- 4 week minimum for transdermal products
- 8 week minimum for oral products

Other parenteral products may require washout periods as long as 6 months.

### **3.4 Concomitant Treatments**

#### **3.4.1 Prohibited and/or Restricted Treatments**

The following medications are prohibited during the study (unless utilized to treat a drug related adverse event):

█ [REDACTED]

█ [REDACTED]

█ [REDACTED]

Prior radiotherapy must have been completed at least 2 weeks prior to starting study treatment. See Section 3.4.3 for guidance on concomitant palliative radiotherapy.

#### **3.4.2 Other Restrictions and Precautions**

Subjects with active, known or suspected autoimmune disease are excluded. Subjects with type I diabetes mellitus, hypothyroidism only requiring hormone replacement, skin disorders (such as vitiligo, psoriasis, or alopecia) not requiring systemic treatment, or conditions not expected to recur in the absence of an external trigger are permitted to enroll.

Subjects with a condition requiring systemic treatment with either corticosteroids (> 10 mg daily prednisone equivalent) or other immunosuppressive medications within 14 days of starting treatment are excluded. Inhaled or topical steroids, and adrenal replacement steroid doses > 10 mg daily prednisone equivalent, are permitted in the absence of active autoimmune disease.

#### **3.4.3 Permitted therapies**

Subjects are permitted the use of topical, ocular, intra-articular, intranasal, and inhalational corticosteroids (with minimal systemic absorption). Adrenal replacement steroid doses > 10 mg daily prednisone are permitted. A brief (less than 3 weeks) course of corticosteroids for

prophylaxis (eg, contrast dye allergy) or for treatment of non-autoimmune conditions (eg, delayed-type hypersensitivity reaction caused by a contact allergen) is permitted. Steroid treatment specified as  $\leq 16$  mg dexamethasone PO daily tapered in  $\leq 4$  weeks is allowed only for the treatment of brain edema.

Concomitant palliative and supportive care for disease related symptoms (including bisphosphonates and RANK-L inhibitors) is allowed if initiated prior to first dose of study therapy.

### **3.4.3.1 Focal Palliative Radiation**

The potential for overlapping toxicities with radiotherapy and nivolumab currently is not known. Therefore, palliative radiotherapy is not recommended while receiving nivolumab. If palliative radiotherapy is required for bone metastases then nivolumab should be withheld for at least 1 week before, during, and 1 week after radiation. Subjects should be closely monitored for any potential toxicity during and after receiving radiotherapy, and AEs should resolve to Grade  $\leq 1$  prior to resuming nivolumab. Only bone lesions may receive palliative radiotherapy. Details of palliative radiotherapy should be documented in the source records and electronic case report form (eCRF). Details in the source records should include: dates of treatment, anatomical site, dose administered and fractionation schedule, and adverse events. Subjects receiving limited field palliative radiation therapy will be considered to have unequivocal progression of disease in the non-target lesion. Symptoms requiring palliative radiotherapy should be evaluated for objective evidence of disease progression. Administration of additional nivolumab to subjects who received limited field palliative radiation should follow guidelines specified in [Section 4.5.4, Treatment beyond Disease Progression](#)

### **3.4.3.2 Palliative brain radiation**

The potential for overlapping toxicities with brain radiotherapy and nivolumab is not known. Therefore palliative brain radiotherapy is not recommended while receiving nivolumab.

Subjects receiving limited field palliative brain radiation therapy will be considered to have unequivocal progression of disease in the non-target lesion. Administration of additional nivolumab to subjects who received limited field palliative radiation should follow guidelines specified in [Section 4.5.4, Treatment beyond Disease Progression](#).

If subjects require palliative brain radiation, nivolumab will be held for at least one week prior to brain radiation, during and 2 weeks following radiation. Subjects should be closely monitored for potential toxicity during and after receiving radiotherapy and AEs should resolve to Grade  $\leq 1$  prior to resuming treatment with nivolumab.

### 3.5 Discontinuation of Subjects following any Treatment with Study Drug

Subjects MUST discontinue investigational product (and non-investigational product at the discretion of the investigator) for any of the following reasons:

- Subject's request to stop study treatment
- Any clinical adverse event (AE), laboratory abnormality or intercurrent illness which, in the opinion of the investigator, indicates that continued participation in the study is not in the best interest of the subject
- Termination of the study by Bristol-Myers Squibb (BMS)
- Loss of ability to freely provide consent through imprisonment or involuntarily incarceration for treatment of either a psychiatric or physical (eg, infectious disease) illness
- Study specific criteria for discontinuation of treatment with nivolumab are presented in [Section 4.5.4.1](#).

In the case of pregnancy, the investigator must immediately notify the BMS Medical Monitor/designee of this event. In most cases, the study drug will be permanently discontinued in an appropriate manner. If the investigator determines a possible favorable benefit/risk ratio that warrants continuation of study drug, a discussion between the investigator and the BMS Medical Monitor/designee must occur.

All subjects who discontinue study drug should comply with protocol specified follow-up procedures as outlined in [Section 5](#). The only exception to this requirement is when a subject withdraws consent for all study procedures including post-treatment study follow-up or loses the ability to consent freely (ie, is imprisoned or involuntarily incarcerated for the treatment of either a psychiatric or physical illness).

If study drug is discontinued prior to the subject's completion of the study, the reason for the discontinuation must be documented in the subject's medical records and entered on the appropriate case report form (CRF) page.

**NOTE: A 4-week washout (minimum) of nivolumab is recommended for subjects who are discontinued from treatment with nivolumab for any reason and are being considered for treatment with mTOR inhibitor.**

### 3.6 Post Study Drug Study Follow up

In this study, safety is a key endpoint of the study. Post study follow-up is of critical importance and is essential to preserving subject safety and the integrity of the study. Subjects who discontinue study drug must continue to be followed for collection of outcome and/or survival follow-up data as required and in line with Section 5 until death or the conclusion of the study.

#### 3.6.1 *Withdrawal of Consent*

Subjects who request to discontinue study drug will remain in the study and must continue to be followed for protocol specified follow-up procedures. The only exception to this is when a subject specifically withdraws consent for any further contact with him/her or persons previously authorized by subject to provide this information. Subjects should notify the investigator of the decision to withdraw consent from future follow-up **in writing**, whenever possible. The

withdrawal of consent should be explained in detail in the medical records by the investigator, as to whether the withdrawal is from further treatment with study drug only or also from study procedures and/or post treatment study follow-up, and entered on the appropriate CRF page. In the event that vital status (whether the subject is alive or dead) is being measured, publicly available information should be used to determine vital status only as appropriately directed in accordance with local law.

### **3.6.2 Lost to Follow-Up**

All reasonable efforts must be made to locate subjects to determine and report their ongoing status. This includes follow-up with persons authorized by the subject as noted above. Lost to follow-up is defined by the inability to reach the subject after a minimum of three documented phone calls, faxes, or emails as well as lack of response by subject to one registered mail letter. All attempts should be documented in the subject's medical records. If it is determined that the subject has died, the site will use permissible local methods to obtain the date and cause of death.

If investigator's use of third-party representative to assist in the follow-up portion of the study has been included in the subject's informed consent, then the investigator may use a Sponsor-retained third-party representative to assist site staff with obtaining subject's contact information or other public vital status data necessary to complete the follow-up portion of the study. The site staff and representative will consult publicly available sources, such as public health registries and databases, in order to obtain updated contact information. If after all attempts, the subject remains lost to follow-up, then the last known alive date as determined by the investigator should be reported and documented in the subject's medical records.

